Cover Page

Type of Document: Study Protocol

Official Title of the study: Integrating Alcohol Myopia and Objectification to Understand Sexual Assault

NCT number: NCT03956238

Date of document: 2-28-20

Study 1: Sexual Objectification and Alcohol-Involved Sexual Aggression (Aim 1)

Participants and procedures. Study 1 will utilize a mixed model experimental design with intoxication (alcohol, placebo control) as the between-participants factor and eye tracking and implicit association tests used to assess objectification as within-participants factors. We expect the behavioral manifestations of myopia—impaired attention and sexual objectification— will emerge in the intoxication condition compared to the placebo control condition. Specifically, community men (n = 150) will come to the lab for a study on “alcohol and perceptions” and be randomized to consume a moderate-dose alcohol or placebo drink, after which they will complete the attention, objectification, and sexual aggression measures.

Alcohol administration. Standard alcohol administration procedures used by the PIs in prior studies (e.g., Watkins, DiLillo, & Maldonado, 2015) will be employed. Men in the alcohol condition will be administered a dose of .90 g(amount of alcohol)/kg(men’s weight) of 95% alcohol U.S. Pharmacopoeia (USP) mixed at a 1:5 ratio with a mixer to achieve a target BAC of at least .08%. Four milliliters of alcohol will be added to the mixer and alcohol will be sprayed on the rim of placebo beverages. All participants will have up to 30 minutes for beverage consumption. For participants in the alcohol condition this will be followed by a 20-minute absorption period. Because the effectiveness of alcohol placebo manipulations tends to diminish starting at about 30 minutes after beverage consumption (Bradlyn & Young, 1983), participants in the placebo condition will have a shorter, 10-minute absorption period.

Attentional capacity. Reduced attentional capacity associated with alcohol myopia will be assessed with the 5-item Mindful Attention Awareness Scale-State version (MAAS-S, Brown & Ryan, 2003). The MAAS-S assesses mindful attention (or lack thereof, I was doing something automatically without being aware of what I was doing) in the present moment or recent past (0 = not at all, 3 = somewhat, 6 = very much). The MAAS has high internal reliability ($\alpha = .92$) and demonstrates construct validity through associations with decreased attentional capacity on the operation span task (Black, Semple, Pokhrel, & Grenard, 2011). Within our myopia framework, we expect intoxication will cause self-reported difficulty paying attention.

Objectification. Given the central role of objectification in this model, this construct will be assessed multi-modally, using behavioral, implicit, and self-report measures (to capture explicit as well as covert attitudes of which people may be relatively unaware or fail to report due to social desirability). Behavioral assessment will occur with the Eye-Tracking Objectification Task ([name] et al., 2013), to assess objectifying gazes. A portable eye-tracking system is used to measure participants’ gazes toward a woman. Specifically, men are told that they are completing a study of media preferences with another participant, an attractive woman wearing revealing clothing. In a series of scripted interactions with the woman, the participant learns that the woman dislikes media with sexual content (which serves as the foundation for the sexual aggression measure, see below). Of interest here will be participants’ gazes toward the woman’s face and body (and sexual body parts in particular, e.g., breasts). Within the context of the myopia framework, attention to the woman’s body represents a provoking cue, whereas attention to the woman’s face represents an inhibiting cue. Intoxication is expected to increase objectifying gazes.

Participants will also complete the Female Object Brief-Implicit Association Task (female object B-IAT, Rudman & Mescher, 2012), which provides a measure of implicit objectification of women (associating women more with objects vs. humans). Implicit associations are assessed by presenting words from different categories (e.g., women, objects, humans) and asking people to press the same response key for two categories of words (e.g., pressing “e” whenever

a “woman” word [e.g., female] or an “object” word [e.g., tool] appears on the screen vs. pressing “e” whenever a “woman” word or a “human” word [e.g., person] appears). Making a response is easier (and thus faster) when closely related constructs share the same response key. Therefore, quicker response times when woman and object (vs. human) words are paired represents more implicit objectification. We expect intoxication to cause faster reaction times when women and object words are paired and slower reaction times for pairings of women and human words.

The Other-Objectification Questionnaire (modified from Grabe, Rutledge, Cook, Andersen, & Arndt, 2005; Curran, 2005), which assesses the frequency (6=very frequently, 1=never) with which the male participant objectified the female confederate (e.g., I focused more on her body than our conversation). Scores are averaged with higher scores representing more objectification of women. We expect intoxication to cause more weight to be placed on women’s objectifying compared to human attributes in men’s evaluations.

Sexual aggression. To assess sexual aggression, participants will complete the Laboratory Analogue of Sexual Aggression (Parrott et al., 2012) based on Hall, Hirschman, and Olivier (1994). Following the ostensible interaction in which the participant learns that the female participant dislikes media with sexual content, men then select one clip—containing either a man and a woman having sexual intercourse or a similar clip without sexual content—for the woman to watch based on still shots and synopses. Choosing the sexual (vs. non-sexual) clip represents sexual aggression. Although perpetrators may justify their choices (e.g., reasoning that the woman may not like sexual content in general, but that she would like this sexual content in particular), such responses fall under the CDC definition of sexual violence (i.e., subjecting a woman to an unwanted sexual experience). Validity of the paradigm is supported by expected positive associations between selection of the sex video and self-reported history of sexual aggression perpetration, adversarial heterosexual beliefs, hostility toward women, and hostile sexism (Parrott et al., 2012). We expect intoxication to cause more sexual aggression.

Study 2: Self-Objectification and Alcohol-Involved Sexual Victimization (Aim 2)

Self-objectification. Similar to sexual objectification for men, self-objectification will be assessed in three complementary ways. A portable eye-tracking system will be used to measure participants' gazes toward their own bodies. Specifically, a mirror will be present in the room during the objectifying gaze lab paradigm. While women are interacting with the male confederate and shortly thereafter, women's gazes toward their own faces and bodies will be assessed with a portable eye tracker. Intoxication and objectification from the male confederate is expected to increase self-objectifying gazes.

Participants will also complete the 10-item Self-Objectification Questionnaire (SOQ; Noll & Fredrickson, 1998). Participants rank order objectifying appearance (e.g., sex appeal, appearance) and non-objectifying, human (e.g., health, stamina) attributes in order of importance (0 = least, 9 = most) to their self-concept. Rankings on non-observable, internal attributes are subtracted from observable, objectifying attributes with higher scores representing more self-objectification. The SOQ is a widely used measure of self-objectification with demonstrated validity (Calogero, 2011). We expect that intoxication and objectification will cause more self-objectification on the SOQ.

Similar to Study 1, participants will also complete the Self-Object Brief-Implicit Association Task (self-object B-IAT; Morris, Goldenberg, & Heflick, 2014), which provides a measure of implicit self-objectification (associating the self more with objects than humans). With the Self-Object B-IAT, "self" (instead of "woman") words (e.g., me, self) are paired with object words or human words. Faster response times when self and object (vs. human) words share a response key represents more implicit self-objectification. We expect intoxication and objectification to cause more self-objectification on the B-IAT.

Risk for sexual victimization. Due to the ethical proscriptions against replicating sexual victimization in the lab, we will assess risk for victimization using the Risk Perception Survey (RPS; Messman-Moore & Brown, 2006). The RPS consists of vignettes depicting forced sexual intercourse. The vignettes include clear (sexual comments, male persistence) and ambiguous (alcohol consumption, physical isolation) risk factors. They contain chronological statements that become progressively riskier as the man increases his coercion. Respondents imagine themselves interacting with the man and the RPS yields a "leave" variable, which reflects the point at which the participant indicates she would leave. We expect impaired risk perception as indicated by higher "leave" values when women are intoxicated and objectified.

Objectification and Alcohol-Involved Sexual Assault: Critical Moderators (Aim 3).

To address Aim 3, participants in Study 1 and Study 2 will complete measures of key moderators online prior to coming to the lab. In Study 1 men will complete the 10-item Sexual Experiences Survey-Short Form Perpetration (SES-SFP; Koss et al., 2007). The SES-SFP assesses the frequency (0 to 3+) of unwanted sexual contact, coercion, attempted rape, and rape. Men will also complete the 10-item Other-Objectification Questionnaire (OOQ) in which

they will rank order the importance of 10 objectifying attributes (e.g., sex appeal) and humanizing, internal attributes to assess overall objectification of women (Noll & Fredrickson, 1998; Grabe et al., 2005; e.g., relative importance of sex appeal vs. well-being, internal states, attributes in women). The ranking for the human attributes is subtracted from the ranking of the objectifying attributes with higher numbers indicating greater objectification of women.

Women in Study 2 will complete the 10-item Self-Objectification Questionnaire (SOQ; Noll & Fredrickson, 1998) that uses the same items, response format, and scoring procedure as the OQ, except people are asked to rank the objectifying and human attributes in themselves to assess self-objectification. Sexual victimization will be assessed with the 10-item Sexual Experiences Survey-Short Form Victimization; SES-SFV; Koss et al., 2007), which assesses the frequency of unwanted sexual advances using the same format as the SES-SFP, but with items worded for victimization rather than perpetration.

Both men and women will complete the 18-item Sex-Related Alcohol Expectancies Scale (SRAES, Dermen & Cooper, 1994), that assesses the degree to which people associate alcohol consumption with sexual disinhibition and risk (e.g., I have sex with people whom I wouldn't have sex with if I were sober) on 6-point scales (1 = strongly disagree, 6 = strongly agree). The SRAES is psychometrically sound including adequate internal consistency reliability ($\alpha = .70 - .83$) and is correlated with alcohol use and sexual risk-taking (Dermen & Cooper, 1994). Men and women will also complete the 19-item Rape Myth Acceptance Scale (RMAS, Burt, 1980), which assesses people's support of rape myths (e.g., Any healthy woman can successfully resist a rapist if she really wants to) on 7-point scales (1 = strongly disagree, 7 = strongly agree).

We expect the predicted effects to be most pronounced for men high on objectification and with a history of sexual assault perpetration (Study 1) and for women high on self-objectification and with a history of sexual assault victimization (Study 2). We also expect these effects to be more exaggerated for men (Study 1) and women (Study 2) high in sex-related alcohol expectancies and rape myth acceptance.

Cover Page

Type of Document: Statistical Analysis Plan

Official Title of the study: Integrating Alcohol Myopia and Objectification to Understand Sexual Assault

NCT number: Not yet assigned

Date of document: 5-10-19

Statistical Analysis Plan

All analyses for Study 1 and 2 will be conducted using Mplus v. 7.4 (Muthén & Muthén, 2015), except descriptive statistics and multivariate analysis of variance models to investigate participant differences between intoxication condition groups (i.e., alcohol, placebo control), as well as order effects and repeated measures effects for the Eye-Tracking Objectification Task and the Implicit Association Task, will be examined using SAS v. 9.4 (SAS Institute, 2014). Manipulation checks will be assessed prior to analyses and appropriate controls (e.g., key demographics such as sexual orientation, race/ethnicity) will be included in the models. Study 1 tests the hypotheses for Aim 1 that intoxication causes more aggression in men (H1a), more impaired attention and objectification (H1b), that impaired attention and objectification mediate the relation between alcohol and aggression (H1c). Hypothesis 1a will be tested by regressing the measures of sexual aggression on intoxication (alcohol vs. placebo control) groups. Hypothesis 1b will be tested by regressing the measures of impaired attention and objectification separately on intoxication condition. Hypothesis 1c will be tested by simultaneously regressing the impaired attention measures on intoxication condition, the objectification measures on the impaired attention measures and intoxication condition, and the aggression measure on the impaired attention, objectification, and intoxication condition measures. The mediated effect of intoxication condition on aggression through each measure of impaired attention and of objectification, as well as the overall mediated effect through all measures, will be estimated using the MODEL INDIRECT statement in Mplus. Mediation will be tested using the bias-corrected bootstrap test (1,000 samples, MacKinnon, 2008).

Study 2 tests the hypotheses for Aim 2 that intoxication condition (i.e., alcohol, placebo control) and objectification condition (i.e., objectifying gazes, eye contact control) each independently cause more victimization risk in women (H2a) and that these two factors interact; the highest victimization risk will occur in women who consumed alcohol and were sexually objectified. Likewise, intoxication and sexual objectification will interact to cause more impaired attention and self-objectification (H2b) with the higher levels occurring for the women who consumed alcohol and were sexually objectified than for women in the other experimental conditions. Finally, Study 2 tests whether impaired attention and self-objectification mediate the relation between alcohol, sexual objectification, and victimization risk (H2c). Hypotheses 2a-c will be tested in the same manner as Hypotheses 1a-c but with alcohol condition, objectification condition, and the interaction between these factors as predictors in the regression, the objectification measures replaced with self-objectification measures, and the aggression measure replaced with the victimization risk perception measure. Alternative models also will be tested. For example, in Study 2, separate indirect paths for both attention and self-objectification between alcohol and sexual victimization risk will be included, assessing whether self-objectification adds explanatory value beyond impaired attention and vice versa. In addition, mediation can be tested independently for each of the four experimental condition groups (e.g., alcohol-objectifying gazes) to determine if the same mechanisms are working for each group.

Since the majority of the moderation hypotheses for Aim 3 involve manifest, continuous variables, moderation will be tested using the conditional process model framework (Hayes, 2013) rather than multi-group structural equation methods. The conditional process model framework involves taking the mediation models from Aims 1 and 2, and adding the two-way interactions between measures of myopia (impaired attentional capacity and sexual and self-objectification) and the moderators. We hypothesize, (a) prior objectification of women by men and (b) self-objectification in women to moderate the relation between impaired attention and situational sexual and self-objectification. Specifically, we expect impaired attention to predict sexual objectification in men, but these effects should be particularly pronounced for men who chronically objectify women. Likewise, we expect impaired attention to predict self-objectification in women, but that these effects should be particularly pronounced for women who chronically self-objectify. We also expect histories of sexual assault perpetration (men), or

sexual victimization history (women), as well as, sex-related alcohol expectancies and rape myth acceptance to emerge as significant moderators of the relation between objectification and assault. Specifically, we expect sexual objectification to predict sexual aggression perpetration in men and self-objectification to predict victimization risk in women, but these effects should be particularly pronounced for people with a history of sexual assault (perpetration in men, victimization in women), as well as for people who endorse more rape myths and those who hold higher sex-alcohol expectancies. All continuous variables (i.e., all variables except the dichotomous measure of aggression in Study 1) will be grand mean centered prior to creating the interaction terms to improve interpretability as recommended by Cohen, Cohen, West, and Aiken (2003). The process will then be repeated for the measures of objectification and the moderator variables. Given the correlations between the moderator variables, the two-way interactions will be examined individually first. All significant interactions will be added to the model simultaneously to examine whether moderation remains. Type I error inflation across models will be controlled for using the Scheffe correction and no effects that explain less than 1% of the total variance will be considered important, regardless of statistical significance.

Missing data. Because the proposed studies are lab experiments, large amounts of missing data are unexpected. Data missing due to equipment malfunctions are missing completely at random (MCAR) and data missing due to nonresponses from participants will be considered missing at random (MAR). The methods for dealing with MCAR and MAR data are full information maximum likelihood (FIML) and multiple imputation (Enders, 2010). By default, Mplus uses FIML, so FIML will be used here for all analyses. Also, bias analyses will be conducted to examine demographics of people who participated in our study compared to people who were recruited for the study, but did not meet the inclusion criteria or who did not agree to participate in our study.

Statistical power. A single mediator model with standardized coefficients of $a=b=.26$ (approximately halfway between a small and medium effect as defined by Cohen, 1988) and $ab=.0676$ requires 148 participants to have statistical power of .80 for the bias-corrected bootstrap test (Fritz & MacKinnon, 2007). The mediation models for Aims 1 and 2 have two mediators entered serially (i.e., attentional impairment and objectification), however, with multiple measures of objectification. When X is dichotomous and two mediators are entered serially, 150 participants provide approximately .82 power to find a standardized mediated effect between .05 and .10 using the bias-corrected bootstrap test (Taylor, MacKinnon, & Tein, 2008) – a standardized mediated effect made up of three medium effects ($a=b_1=b_2=.39$) is equal to .06. Using multiple objectification measures slightly decreases individual effects due to partialling, but this will not affect the power calculations because they are based on partial effects. Research has found that alcohol predicts 10% of the objectification variance, and alcohol and objectification together predict 22% of the sexual assault variance ([name], et al., 2014; see also Haikalis et al., 2015). These are medium and large effects, so sample sizes of 150 (Study 1) and 210 (Study 2) will provide adequate power to test Aims 1 and 2. The power analyses for Aim 3 are different because they involve moderation effects in the context of mediation, which Hayes (2013) terms a conditional process model. An issue with detecting moderator effects is the small amount of variance explained by an interaction relative to a main effect (McClelland & Judd, 1993). No work on power for conditional process models has been conducted, but using G*Power (Faul, Erdfelder, Lang, & Buchner, 2007) to conduct a sensitivity analysis found that a sample size of 150 (Study 1) would provide .80 power to detect a moderation effect of $f^2 = .053$ (slightly larger than a small effect of $f^2 = .02$, Cohen, 1988) when the moderation term, a main effect term (for the 2 alcohol intoxication conditions), and two additional predictors are included in the model. A second sensitivity analysis found that a sample size of 210 (Study 2) would provide .80 power to detect a moderation effect of $f^2 = .044$ when the moderation term being tested, two main effects terms (one for the 2 objectification conditions and one for the 2 alcohol conditions), two interaction terms (between the intoxication

and objectification factors), and two additional predictors are included in the model. This is equivalent to testing moderation of the relation between objectification and aggression/victimization risk in the mediation models, so sample sizes of 150 (Study 1) and 210 (Study 2) will allow adequate power to test Aim 3 (Figure 3).

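### With 1,000 bootstrap draws, H1c and H2c mediation verdicts whose interval limit lies near zero can change with the random seed; more draws and a stated seed would cost only computing time

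*SAP*

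**What the plan says.** The first paragraph of the SAP sets the test for Hypothesis 1c: "Mediation will be tested using the bias-corrected bootstrap test (1,000 samples". It covers the indirect effect through each attention and objectification measure, "as well as the overall mediated effect through all measures". The next paragraph carries the method to Study 2: "Hypotheses 2a-c will be tested in the same manner as Hypotheses 1a-c but with alcohol condition, objectification condition, and the interaction between these factors". Study 2 therefore has three design terms where Study 1 has one.

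The number of mediators follows from the protocol. Attention is measured by one scale. For objectification in Study 1, "this construct will be assessed multi-modally, using behavioral, implicit, and self-report measures". In Study 2, "self-objectification will be assessed in three complementary ways". The Study 1 outcome is binary; the SAP's moderation text calls it "the dichotomous measure of aggression in Study 1". The planned sizes are 150 and 210.

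Neither document gives a random seed, a check on Monte Carlo error, a significance level for the mediation intervals, or a count of the indirect effects to be judged.

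**The concern.** Whether mediation is claimed depends on whether a bootstrap interval excludes zero. With 1,000 draws, each 95% limit is read from about the 25th most extreme draw, or from a different rank once the bias correction moves the cut-point. If the limit lies close to zero, another set of draws from the same data may put it on the other side. The more indirect effects a model yields, the likelier it is that one of them is in that position.

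The mechanistic conclusions of Aims 1 and 2 are at stake: some borderline verdicts would depend on the seed rather than on the data. This concerns the number of draws only. It would apply equally to a percentile bootstrap and is separate from the choice of bias-corrected intervals.

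**Working it through.** **Inputs from the documents.** 1,000 draws, bias-corrected; "sample sizes of 150 (Study 1) and 210 (Study 2"); one attention measure and three objectification measures per study; one condition contrast in Study 1 and three design terms in Study 2; planning paths of .26 and .39 (SAP, Statistical power).

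**Assumptions not in the documents.** Two-sided .05; residual correlation .3 among the objectification measures; 50% (or 25%) choosing the sexual clip; complete data; no covariates.

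**The SAP's own figures.** Simulating the single-mediator model (N = 148, a = b = .26, 1,500 datasets, 1,000 draws) gives power .819 against the stated .80. The product .39 × .39 × .39 = .0593 matches the stated .06. The serial power of about .82 was not matched at .39 with a condition coded ±1 (simulated .996; paths of .26 gave .814). That depends on how the condition is scaled and does not bear on this point.

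**Number of verdicts.** Attention 1 + objectification 3 + serial 3 + overall 1 = 8 in Study 1; 8 × 3 = 24 in Study 2. Without separate serial paths: 5 and 15.

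**Monte Carlo error.**
- 1,000 draws: sqrt(.025 × .975 / 1,000) = .0049. Doubled for two sides, with ±1.96 SE: .05 ± 2 × 1.96 × .0049 = .05 ± .019, so about .03 to .07.
- 10,000 draws: sqrt(.025 × .975 / 10,000) = .0016, giving .05 ± .006, so about .044 to .056.

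This leaves out the noise in the bias-correction constant, which is estimated from the same draws.

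**Benchmark for one effect with .80 power (normal approximation).** The test statistic has density .28 at 1.96. The standard normal density there is .0584, so the limit has Monte Carlo SE .0049/.0584 = .084 z-units. Two runs disagree with probability about .28 × .084 × sqrt(2) × .798 = .027. If all effects had .80 power and were independent, at least one of 8 would differ in about 19% of datasets and one of 24 in about 48%. At 10,000 draws these become about 7% and 18%.

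**Simulation of the planned models.** 400-600 datasets per scenario, six independent 1,000-draw runs on each; the result is the share of run pairs in which at least one verdict differs.

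| Scenario | At least one verdict differs |
|---|---|
| Study 1 (binary outcome, 8 verdicts), all paths null | 1% |
| Study 1, serial path only | 18-25% |
| Study 1, all paths non-zero | 23-36% |
| Study 2 (24 verdicts), all paths null | 4% |
| Study 2, all paths .14 / .20 / .26 / .39 | 60% / 56% / 23% / 0.4% |
| Study 2, serial path only, .26 / .39 | 34% / 29% |
| Study 2, condition effects halved: .26 / .39 / serial .39 | 61% / 38% / 37% |

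The Study 2 rows with non-zero paths use effect coding. With no true interaction the non-null range is 12-53%; with dummy coding it is 19-44%. Counting 5 and 15 verdicts, the non-null ranges are 7-27% (Study 1) and 0.2-49% (Study 2). A single given verdict flips in at most about 6% of datasets (usually 1.5-5.5% in non-null Study 1 scenarios, less in several Study 2 ones). The overall mediated effect flips in 0-8%.

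**At 10,000 draws.** Study 1 (200 datasets per scenario): 7-14% in non-null scenarios, against 19-34% for the same scenarios at 1,000. Study 2 was not simulated with this set-up. Scaling the worst case gives 1 − (1 − .60)^(1/sqrt(10)) = .25, so roughly 25%.

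**The case against.** The strongest reply is that 1,000 draws do not harm the test's operating characteristics, and this stands. In a single-mediator check (N = 148, 1,200 datasets per scenario), power at a = b = .26 was .824 and .832 in two 1,000-draw runs, against .825 with 5,000 draws. With a = .26 and b = 0, rejection was .073 against .070. Two runs disagreed in 4.1% and 1.5% of datasets in those scenarios.

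It is also fair to say that no decision in the SAP is defined as any one of 8 or 24 verdicts differing, and that the SAP states neither count. The family-wise figures measure overall repeatability; they are not error rates for a hypothesis.

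Three stronger readings are tempting, and the documents do not support them:
- A reader might infer that about half of Study 2 datasets would give a different verdict on re-running. That arises mainly with small paths (.14-.20, or .26 with halved condition effects) and mostly when all 24 effects are counted. At the SAP's planning values, without halving and with effect coding, the range is 0.4-34%.
- A reader might infer that every mediation verdict is unreliable. Only those with a limit near zero are.
- A reader might infer that a second analyst with the same data and code could not reproduce the result. If the code sets a seed, the analyst could; the uncertainty is over a different seed.

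None of this shows that 1,000 draws suffice for a verdict near the cut-off.

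**Conclusion.** The point holds as a matter of repeatability. The plan leaves borderline H1c and H2c verdicts exposed to Monte Carlo error that is cheap to reduce, and it says nothing about how such cases are handled. The effect on any one verdict is small. Across the whole set of indirect effects it is material in Study 1 whenever effects are non-zero. In Study 2 it ranges from negligible to large, so no single percentage describes the plan.

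The sizes rest on the assumed .05 level, the assumed verdict counts, the residual correlation of .3, and path sizes varied from 0 to .39. The arithmetic for the tail area needs only the number of draws and the .05 level. Smaller Study 2 paths are plausible, since the SAP itself notes how little variance interactions tend to explain, but the documents do not fix those sizes.

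**What to change.** In the SAP's Hypothesis 1c text, replace 1,000 samples with at least 10,000, and state that the same number applies to Hypothesis 2c. Prespecify and report the seed. This makes a run reproducible but does not reduce Monte Carlo error; only more draws do that. Add a rule for borderline limits: if a limit still lies within Monte Carlo error of zero, increase the draws until the verdict is stable, and report the number used. The rule is needed because 10,000 draws reduce the instability without removing it.

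It would also help to list the indirect effects that will be judged and the level of their intervals, so that the size of the family is known.

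The cost is computing time only: no new data and no loss of power.

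### H2c has no defined mediated effect: with the alcohol-by-gaze product in the model, alcohol's indirect path depends on a coding the SAP does not state

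*SAP*

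**What the plan says.** For Study 1, the SAP's opening paragraph regresses the mediators on intoxication condition and the outcome on the mediators and condition. The mediated effect through each measure, "as well as the overall mediated effect through all measures, will be estimated using the MODEL INDIRECT statement in Mplus", is tested with a bias-corrected bootstrap of 1,000 samples. Intoxication is the only randomized factor there.

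For Study 2, the SAP states "Hypotheses 2a-c will be tested in the same manner as Hypotheses 1a-c but with alcohol condition, objectification condition, and the interaction between these factors"; all three terms enter the regressions. H2b predicts an interaction on impaired attention and self-objectification, "with the higher levels occurring for the women who consumed alcohol and were sexually objectified than for women in the other experimental conditions". H2c asks whether these measures mediate the relation between alcohol, objectification and victimization risk.

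The SAP gives no numerical coding for either condition. For Aim 2 it names no indirect effect by gaze level and no difference between levels. The only coding-related sentence is in the Aim 3 text: "All continuous variables (i.e., all variables except the dichotomous measure of aggression in Study 1) will be grand mean centered" before interaction terms are formed. An optional analysis would test mediation separately in each of the four cells.

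**The concern.** In a model with a product term, a factor's own coefficient is its effect where the other factor equals zero. Carrying the Study 1 method over therefore does not give the mediated effect of alcohol. It gives a conditional effect, and the condition is set by a coding choice the plan does not make. Two analysts could both follow the SAP, use different codes and reach different answers on H2c from the same data. The code could also be settled after the data are seen.

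Nothing else in the plan closes the gap. The centering sentence belongs to Aim 3 and speaks of continuous variables. Its parenthesis is broader, so whether it reaches the conditions is unclear; if it does, alcohol's path becomes an average over gaze levels. The conditional process models are assigned to Aim 3 and concern the measured moderators. In the four-cell analysis alcohol is constant within each cell, so no alcohol effect can be estimated there.

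**Working it through.** **The plan's own figure.** The SAP's power section gives .80 for a single mediator with a = b = .26 and N = 148, using the bias-corrected bootstrap. Simulation (1,000 trials, 1,000 bootstrap samples) gives .813, so the figure reproduces and the simulation method is sound.

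**What the alcohol path estimates.** Let A be alcohol and G gaze, both coded 0/1 with eye contact = 0:

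M = a0 + a1·A + a2·G + a3·A·G + error, and Y contains b·M.

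- Alcohol's path, eye contact coded 0: a1·b
- Alcohol's path, gaze coded 0: (a1 + a3)·b, the effect among objectified women
- Alcohol's path, gaze coded -1/2 and +1/2: (a1 + a3/2)·b, the average
- Product path: a3·b, the difference between gaze levels

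**Inputs.** N = 210 (Protocol, Study 2) and b = .39 (the SAP's medium path). Assumed: equal cells (52.5 on average), residual SD 1, one mediator, two-sided 5%, and alcohol shifts under gaze of .5, .63 and .8 SD. The middle value is close to the SAP's statement that alcohol predicts 10% of objectification variance: (d/2)² = .10 gives d = .63.

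**Normal approximation.** The b path is detected almost always (z about .39·√205 = 5.6), so power is set by the alcohol-to-mediator path. Standard errors are:

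- effect at one gaze level: √(1/52.5 + 1/52.5) = 2/√105 = .195
- average: 2/√210 = .138
- product: 4/√210 = .276

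For a shift of .63 SD only in the alcohol-plus-gaze cell:

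- Under gaze: z = .63/.195 = 3.23, power Φ(3.23 - 1.96) = .90.
- Average: z = .315/.138 = 2.28, power .63.
- Product: z = .63/.276 = 2.28, power .63.
- Under eye contact: true effect 0, so about the nominal rate.

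**Bias-corrected bootstrap, same pattern, b = .39:**

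| Indirect effect | .5 SD | .63 SD | .8 SD |
|---|---|---|---|
| Alcohol, eye contact coded 0 | .06 | .08 | .04 |
| Alcohol among objectified women | .77 | .90 | .97 |
| Average over gaze levels | .51 | .69 | .84 |
| Product (difference) | .50 | .64 | .84 |

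The dependence on coding also appears at the SAP's smaller path (b = .26, shift .54 SD). Alcohol's own path is significant in 8% of trials with eye contact coded 0, 53% with centered codes and 80% with gaze coded 0.

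**Alcohol keeps half its effect under eye contact (.315 vs .63 SD).**

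- Eye contact coded 0: z = .315/.195 = 1.61, power .36 by approximation; bootstrap runs gave .40 and .46.
- Under gaze: about .91 (bootstrap).
- Average: about .95 (bootstrap); by approximation z = .4725/.138 = 3.42, power .93.
- Difference: z = .315/.276 = 1.14, power .21 by approximation.

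**H2a main effects (additive .39 SD).**

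- 0/1 codes: .39/.195 = 2.00, power .52.
- -1/2, +1/2 codes: .39/.138 = 2.83, power .81.

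**The case against.** The strongest reply is that the product is itself one of the three predictors. Applied to each predictor, the Study 1 method would also return the product's indirect effect, which carries the signal when alcohol acts only under gaze (.50 to .84 above). The SAP does not exclude this. It does not ask for it either: where its alternative models name a path, it runs from alcohol to victimization risk.

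A reader might infer that H2c will miss mediation, or that the plan looks in the wrong half of the sample. The documents do not support that. No coding is stated, and the centering sentence, read by its parenthesis, could reach the conditions and turn alcohol's path into the average.

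A reader might also infer that H2b implies no alcohol effect under eye contact. It requires only that the combined cell be highest. The protocol's Study 2 section on attentional capacity expects intoxication to impair attention with no gaze condition attached, its self-objectification section expects both factors to raise that measure, and H2a gives each factor its own effect on risk. A reduced path is then more in keeping with the documents than a null one.

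Finally, H2c as written is not confined to objectified women. Making it so would be a choice of estimand, and under the half-effect pattern the average does at least as well.

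These points limit the claim. They do not supply the missing coding or the missing target effect.

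**Conclusion.** The point stands as a specification gap with a material consequence. H2c, the mechanism hypothesis of Aim 2, has no defined estimand, because neither the coding nor the deciding indirect effect is given. In the least favorable reading (eye contact coded 0, alcohol acting only under gaze, alcohol's own path taken as the answer) detection falls to about 4-8%, where the effect among objectified women would be found in 77-97%. In the milder pattern it falls to about .40 to .46, against .91 under gaze and .95 for the average. H2a power for .39 SD moves between .52 and .81 on the coding alone.

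The dependence on coding is algebra. The sizes rest on assumed shifts, equal cells, residual SD 1 and one mediator in place of the planned serial model with several measures; simulated values carry an error of a few points.

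**What to change.** Code both conditions -1/2 and +1/2 throughout H2a-c and say so in the Study 2 paragraph, so that the lower-order terms are average effects.

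For H2c, define these quantities in the Mplus model and test them with the planned bias-corrected bootstrap, in place of reading MODEL INDIRECT on the alcohol term alone:

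- alcohol's indirect effect under gaze and under eye contact
- their average
- their difference (the product path)
- the same four for gaze, by beverage condition

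The investigators should then state, before analysis, which of these decides H2c. The average suits a general mediation claim, the effect among objectified women a claim about that group, and the difference a claim that gaze changes the mechanism. The difference has low power if alcohol also acts under eye contact. The SAP should also say whether the Aim 3 centering sentence applies to the conditions.

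The cost is a paragraph of SAP text, a few lines of syntax and more reported quantities. No new data are needed.
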